#### 8.3.6.2 Grade 2 Arrhythmia: No symptoms AND non-urgent intervention indicated

- WITHHOLD further doses of cemiplimab/placebo until clinical and laboratory evaluation are completed and diagnosis and etiology of the symptoms or laboratory abnormalities are defined
- Immediately contact the core team via email at  
[[contact]](mailto:[contact])

- Consult cardiologist immediately
- Consider systemic corticosteroids (starting with 1 mg/kg prednisone or equivalent once per day or dexamethasone 4 mg orally once daily for 4 days; when symptoms improve to Grade 1 or less, steroid taper should be started and continued over no less than 4 weeks in consultation with a cardiologist)

8.3.6.3 Grade 3 Arrhythmia: Non-life-threatening symptoms AND non-urgent intervention indicated

WITHHOLD further doses of cemiplimab/placebo until clinical and laboratory evaluation are completed and diagnosis and etiology of the symptoms or laboratory abnormalities are defined

- Immediately contact the core team via email at [[contact]](mailto:[contact])
- Consult cardiologist immediately
- Treat with moderate-dose steroids (recommend prednisone 240 mg/day orally or methylprednisolone 4 mg/kg/day IV); when symptoms improve to Grade 1 or less, steroid taper should be started and continued over no less than 4 weeks in consultation with a cardiologist
- If no significant response to initial corticosteroid treatment, consider high-dose corticosteroids (recommended methylprednisolone 1 g/day IV); if high-dose corticosteroids used, they should be tapered in consultation with a cardiologist

8.3.6.4 Grade 4 Arrhythmia: Life-threatening arrhythmia OR Urgent intervention indicated

- WITHHOLD further doses of cemiplimab/placebo
- Immediately contact the core team via email at [[contact]](mailto:[contact])
- Immediate hospitalization
- Consult cardiologist immediately
- Treat with high-dose steroids (recommended methylprednisolone 1 g/day IV) in consultation with a cardiologist
- High-dose corticosteroids should be tapered in consultation with a cardiologist

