NOTE C: The core team must be notified within 24 hours by email at [[contact]](mailto:[contact]) regarding any suspected or confirmed irAE of any grade that are considered to be related to study treatment. In such cases, cemiplimab/placebo should be withheld.

NOTE D: Should there be any question about whether an AE is considered an irAE, sites should withhold cemiplimab/placebo and immediately contact one of the protocol chairs (see contact information in [Protocol Team Roster](#) on page 6).

NOTE E: For toxicities that cause DISCONTINUATION of cemiplimab/placebo, future doses of cemiplimab/placebo should not be given to the participant. Whereas, for toxicities that cause WITHHOLDING of cemiplimab/placebo, there is potential for continued/future doses to be given once the toxicity(ies) in question have been further investigated by site investigator and the study core team.

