8.3.6.6 Grade 2 Heart Failure: Symptoms with mild to moderate activity or exertion

- WITHHOLD further doses of cemiplimab/placebo until clinical and laboratory evaluation are completed and diagnosis and etiology of the symptoms or laboratory abnormalities are defined
- Immediately contact the core team via email at [[contact]](mailto:[contact])
- Consult cardiologist immediately
- Initiate systemic corticosteroids (starting with 1 mg/kg prednisone or equivalent once per day or dexamethasone 4 mg orally once daily for 4 days); when symptoms improve, steroid taper should be started and continued over no less than 4 weeks in consultation with a cardiologist.
- If no response to initial corticosteroids, consider moderate dose steroids (recommend: prednisone 240 mg/day orally or methylprednisolone 4 mg/kg/day IV); when symptoms improve to Grade 1 or less, steroid taper should be started and continued over no less than 4 weeks in consultation with a cardiologist.
- Repeat ECG within 24 hours notification
- Obtain echocardiogram
- Proceed with standard of care diagnostics and management for new onset heart failure

8.3.6.7 Grade 3 Heart Failure: Symptoms at rest or with minimal activity or exertion (e.g., hypoxemia) OR intervention indicated (e.g., oxygen)

- WITHHOLD further doses of cemiplimab/placebo until clinical and laboratory evaluation are completed and diagnosis and etiology of the symptoms or laboratory abnormalities are defined
- Immediately contact the core team via email at [[contact]](mailto:[contact])
- Consult cardiologist immediately
- Initiate moderate dose steroids (recommend prednisone 240 mg/day orally or methylprednisolone 4 mg/kg/day IV); when symptoms improve to Grade 1 or less, steroid taper should be started and continued over no less than 4 weeks in consultation with a cardiologist.

- If no response to initial corticosteroids, consider high-dose steroids (recommended methylprednisolone 1 g/day IV) in consultation with a cardiologist
- Repeat ECG within 24 hours notification
- Obtain echocardiogram
- Proceed with standard of care diagnostics and management for new onset heart failure

8.3.6.8 Grade 4 Heart Failure: Life-threatening consequences OR urgent intervention indicated (e.g., vasoactive medications, ventricular assist device, heart transplant)

- DISCONTINUE further doses of cemiplimab/placebo
- Immediately contact the core team via email at [[contact]](mailto:[contact])
- Consult cardiologist immediately

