- Initiate moderate-dose steroids (recommend prednisone 240 mg/day orally or methylprednisolone 4 mg/kg/day IV); when creatinine improves to Grade 1 or less, steroid taper should be started and continued over no less than 4 weeks in consultation with a nephrologist.
- If no response to initial corticosteroids, consider high-dose steroids (recommended methylprednisolone 1 g/day IV) in consultation with a nephrologist; high-dose corticosteroids should be tapered, if used, in consultation with a nephrologist.

8.3.7.4 Grade 4 Creatinine Abnormality:  $\geq 3.5 \times$  ULN OR increase of  $\geq 2.0 \times$  participant's baseline

- WITHHOLD further doses of cemiplimab/placebo until clinical and laboratory evaluation are completed and diagnosis and etiology of the symptoms or laboratory abnormalities are defined

- Immediately contact the core team via email at [[contact]](mailto:[contact])
- Consult nephrologist immediately
- Obtain urinalysis, erythrocyte sedimentation rate (ESR), complement levels (C3, C4, CH50), anti-DNA levels, and antineutrophil cytoplasmic antibody (ANCA)
- Monitor creatinine every 72 hours
- Obtain renal ultrasound and 24 hour urine studies
- Initiate high-dose steroids (recommended methylprednisolone 1 g/day IV) in consultation with a nephrologist; high-dose corticosteroids should be tapered, if used, in consultation with a nephrologist.

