## 9.0 CRITERIA FOR DISCONTINUATION

### 9.1 Permanent and Premature Treatment Discontinuation

Study treatment is two single infusions of cemiplimab (anti-PD-1 antibody) or placebo. Study treatment should be discontinued for:

- Drug-related toxicity (see [section 8.1](#))
- A Grade 3 or 4 infusion reaction occurs (see [section 8.2](#))
- Discontinuation of ART
- Requirement for prohibited concomitant medications (see [section 5.4](#))
- Pregnancy or breastfeeding
- Request by participant to terminate treatment
- Clinical reasons believed life-threatening by the physician, even if not addressed in [section 8.1](#) of the protocol
- Positive results for antibodies to TPO, GAD65/GAD or islet cell antigen
- An irAE of any grade occurs
- Prolonged need (>7 days) for systemic steroids

NOTE A: Participants who receive one infusion but for whom treatment was discontinued prematurely will be followed on study off treatment per the schedule of events.

NOTE B: If the study participant experiences an irAE after the first infusion of cemiplimab/placebo at entry, study treatment should be discontinued (i.e., the participant would not receive the second infusion).

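### Section 8.3.6.4 withholds dose 2 after a life-threatening arrhythmia where section 9.1 discontinues it, and the two disagree when the event has another cause

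*Protocol*

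**What the plan says.** The relevant text is all in the protocol.

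- **Section 8.3.6.4** is headed "Grade 4 Arrhythmia: Life-threatening arrhythmia OR Urgent intervention indicated". Its dosing line is "WITHHOLD further doses of cemiplimab/placebo", and it stops there. The arrhythmia rules for Grades 1 to 3 (8.3.6.1 to 8.3.6.3) use the same word but add a clause that ends the hold once the work-up is complete and the cause is known.
- **Section 8.0, NOTE E** separates the two dosing words. After DISCONTINUATION no later dose is to be given. By contrast, "for toxicities that cause WITHHOLDING of cemiplimab/placebo, there is potential for continued/future doses to be given" once the site investigator and core team have looked into the toxicity.
- **Section 8.0, guidance on adverse events of special interest** holds infusions for any suspected immune-related event (irAE). It discontinues them if the event is confirmed or cannot be excluded, and allows them to continue if another cause is found.
- **Section 9.1** lists reasons for which study treatment should be discontinued. One is "Clinical reasons believed life-threatening by the physician", and it applies even to matters that section 8.1 does not cover. Others are drug-related toxicity, an irAE of any grade, and a need for systemic steroids beyond 7 days.
- **Section 8.3.6.8**, Grade 4 heart failure, says "DISCONTINUE further doses of cemiplimab/placebo".

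**The concern.** NOTE E makes WITHHOLD and DISCONTINUE different instructions, so the choice of word in an organ section decides whether dose 2 stays available. In 8.3.6.4 the word that keeps dose 2 available is attached to an event that its own heading calls life-threatening, which is the ground on which section 9.1 stops treatment. The neighbouring Grade 4 heart failure rule has nearly the same definition and uses the other word.

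A site with such a participant between day 0 and week 6 would find two current instructions that differ on whether the second infusion can be rescheduled. Nothing in section 8.0 or 9.1 says which prevails. This matters at the most severe grade, in participants who by the protocol's own account receive no direct benefit from the study.

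**Working it through.** No figure is involved, so the check sets the rules side by side.

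**Step 1. Does the definition in 8.3.6.4 meet the 9.1 criterion?** The first limb of the Grade 4 heading is life-threatening arrhythmia, so it meets it by its own words. The second limb, urgent intervention, meets it only if the physician also believes the event life-threatening. The textual conflict is confined to the first limb and to that judgement.

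**Step 2. Follow the participant by attribution.**

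| Attribution of a life-threatening arrhythmia after dose 1 | 8.3.6.4 with NOTE E | Other rules | Dose 2 |
|---|---|---|---|
| Suspected irAE, still under investigation | Withheld | 6.3.5 bars the second infusion | Barred for now |
| irAE confirmed or not excluded | Withheld | 8.0 and 9.1 discontinue | Barred |
| Related to study drug, not an irAE | Withheld | 9.1 drug-related toxicity | Barred |
| Another cause, systemic steroids needed for more than 7 days | Withheld, later dose possible | 8.0 allows continuation; 9.1 steroid criterion discontinues | Barred under 9.1 |
| Another cause, steroids for 7 days or less, or none | Withheld, later dose possible | 8.0 allows continuation; 9.1 life-threatening criterion discontinues | **Opposite answers** |

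The last row is where the conflict mainly sits.

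**Step 3. Compare the other Grade 4 rules.** Sections 8.2 to 8.6 contain 15 rules that name Grade 4 and carry a dosing word.

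- DISCONTINUE (11): infusion reaction 8.2.4, diarrhea or colitis 8.3.1.4, hepatic 8.3.2.4, adrenal 8.3.4.4, pulmonary 8.3.5.4, heart failure 8.3.6.8, diabetes 8.3.9.2, uveitis 8.4.4, dermatitis 8.5.4, platelets 8.6.1.4, neutrophils 8.6.2.4.
- WITHHOLD (4): arrhythmia 8.3.6.4, creatinine 8.3.7.4, altered mental status, weakness or seizures 8.3.8.1, headache or neurosensory alteration 8.3.8.3.

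11 + 4 = 15. The thyroid rule (8.3.3.1) is also WITHHOLD but is not split by grade, so it is not counted.

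**Step 4. Do the other three WITHHOLD rules conflict with 9.1?** Not by their text. Grade 4 creatinine is defined by multiples of the upper limit of normal or of baseline, and its dosing line carries the end condition: "WITHHOLD further doses of cemiplimab/placebo until clinical and laboratory evaluation are completed and diagnosis and etiology of the symptoms or laboratory abnormalities are defined". The two neurologic rules give no life-threatening definition in the protocol. These three differ from the majority pattern, and whether that is intended is a fair question. Only 8.3.6.4 combines a life-threatening definition with WITHHOLD and no end clause of its own.

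**The case against.** The strongest reply is that WITHHOLD is only the immediate step. Section 8.3.6 concerns suspected myocarditis, so a site would hold the drug, investigate, and then apply the general irAE rule in 8.0 and the list in 9.1. NOTE E speaks only of a potential for later doses and does not authorise one against 9.1. The 9.1 steroid criterion closes dose 2 for many treated participants, since 8.3.6.4 itself calls for high-dose steroids with a taper. Section 8.0 also describes its content as guidance subject to clinical judgement and mandates discontinuation criteria only for toxicities related to study treatment, while the 9.1 criterion rests on what the physician believes.

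Much of this stands, and it removes every row of the table but the last as a practical problem. It does not settle the last row. Limiting mandated criteria to related toxicities does not reconcile 8.0 with a 9.1 criterion that carries no such limit, and no sentence ranks the two sections.

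Three stronger readings are tempting, and the protocol does not support them.

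- *A participant with a related Grade 4 arrhythmia could be re-dosed after a safety pause under section 10.5 is lifted.* A related event is already excluded from dose 2 by 9.1. An irAE is excluded by 8.0 and 9.1, and by 6.3.5 while it is being investigated. Rescheduling after a pause overrides none of these.
- *The choice of word changes replacement or the efficacy population.* Sections 6.2.5, 10.4 and 10.6.2 use receipt of at least 90% of both infusions, and replacement also depends on whether the safety endpoint was met. A participant who does not receive dose 2 is treated alike under either word.
- *Grade 4 creatinine contradicts 9.1, and all parallel Grade 4 sections say DISCONTINUE.* Creatinine is defined by laboratory values, and the two neurologic rules also withhold.

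**Conclusion.** The point holds in a narrow form. For a life-threatening arrhythmia attributed to a cause other than study treatment, 8.3.6.4 with NOTE E and the general rule in 8.0 leave dose 2 possible, while 9.1 says treatment should be discontinued. The different instruction for Grade 4 heart failure in 8.3.6.8, and the missing end clause, make 8.3.6.4 look out of line with its surroundings. The wording of 8.3.7.4, 8.3.8.1 and 8.3.8.3 is an inconsistency to check and not a contradiction of 9.1.

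Few participants are likely to be affected. The protocol's oncology safety table lists 1 autoimmune myocarditis among 757 patients, but that is not the rate of the residual case, which is an arrhythmia with another cause; the protocol gives no rate for it. The conclusion assumes that the physician regards an arrhythmia meeting the first limb of the heading as life-threatening for the purpose of 9.1. No estimate, power figure or analysis population is touched. The point still deserves correction because it concerns a dosing rule at the most severe grade and is easily put right.

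**What to change.** 1. Reconcile 8.3.6.4 with 9.1, with section 8.0 (NOTE E and the irAE rule) and with 8.3.6.8, so that Grade 4 arrhythmia carries one dose-2 instruction, including for an event attributed to another cause.
2. State in section 8.0 which section governs when an organ-specific rule and 9.1 differ.
3. Confirm whether WITHHOLD at Grade 4 is intended in 8.3.7.4, 8.3.8.1 and 8.3.8.3.

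Which clinical rule applies is for the sponsor's medical team. The cost is a clarification memo or letter of amendment, with no effect on sample size, visits or procedures.

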8.3.6.5 Grade 1 Heart Failure: No symptoms AND laboratory or cardiac imaging abnormalities

- Consult cardiologist immediately
- Repeat ECG within 24 hours of notification
- Obtain echocardiogram

- Consider systemic corticosteroids (starting with 1 mg/kg prednisone or equivalent once per day or dexamethasone 4 mg orally once daily for 4 days); when symptoms improve, steroid taper should be started and continued over no less than 4 weeks in consultation with a cardiologist.
- Proceed with standard of care diagnostics and management for new onset heart failure

8.3.6.6 Grade 2 Heart Failure: Symptoms with mild to moderate activity or exertion

- WITHHOLD further doses of cemiplimab/placebo until clinical and laboratory evaluation are completed and diagnosis and etiology of the symptoms or laboratory abnormalities are defined
- Immediately contact the core team via email at [[contact]](mailto:[contact])
- Consult cardiologist immediately
- Initiate systemic corticosteroids (starting with 1 mg/kg prednisone or equivalent once per day or dexamethasone 4 mg orally once daily for 4 days); when symptoms improve, steroid taper should be started and continued over no less than 4 weeks in consultation with a cardiologist.
- If no response to initial corticosteroids, consider moderate dose steroids (recommend: prednisone 240 mg/day orally or methylprednisolone 4 mg/kg/day IV); when symptoms improve to Grade 1 or less, steroid taper should be started and continued over no less than 4 weeks in consultation with a cardiologist.
- Repeat ECG within 24 hours notification
- Obtain echocardiogram
- Proceed with standard of care diagnostics and management for new onset heart failure

8.3.6.7 Grade 3 Heart Failure: Symptoms at rest or with minimal activity or exertion (e.g., hypoxemia) OR intervention indicated (e.g., oxygen)

- WITHHOLD further doses of cemiplimab/placebo until clinical and laboratory evaluation are completed and diagnosis and etiology of the symptoms or laboratory abnormalities are defined
- Immediately contact the core team via email at [[contact]](mailto:[contact])
- Consult cardiologist immediately
- Initiate moderate dose steroids (recommend prednisone 240 mg/day orally or methylprednisolone 4 mg/kg/day IV); when symptoms improve to Grade 1 or less, steroid taper should be started and continued over no less than 4 weeks in consultation with a cardiologist.

- If no response to initial corticosteroids, consider high-dose steroids (recommended methylprednisolone 1 g/day IV) in consultation with a cardiologist
- Repeat ECG within 24 hours notification
- Obtain echocardiogram
- Proceed with standard of care diagnostics and management for new onset heart failure

8.3.6.8 Grade 4 Heart Failure: Life-threatening consequences OR urgent intervention indicated (e.g., vasoactive medications, ventricular assist device, heart transplant)

- DISCONTINUE further doses of cemiplimab/placebo
- Immediately contact the core team via email at [[contact]](mailto:[contact])
- Consult cardiologist immediately
- Initiate high-dose steroids (recommended methylprednisolone 1 g/day IV) in consultation with a cardiologist
- Repeat ECG within 24 hours notification
- Obtain echocardiogram
- Proceed with standard of care diagnostics and management for new onset heart failure

8.3.7 Suspected Immune-related Renal Dysfunction

For participants with worsening renal function, the following should be obtained: repeat BUN, serum creatinine, and serum electrolytes within 48 hours of the first abnormal value. For any suspected immune-related renal toxicity, WITHHOLD further doses of cemiplimab/placebo until diagnostic evaluation has been completed and etiology of the signs and symptoms has been determined.

NOTE: The DAIDS AE Grading Table, corrected Version 2.1, July 2017, for grading creatinine should be used, and can be found on the DAIDS RSC website at <https://rsc.niaid.nih.gov/clinical-research-sites/daids-adverse-event-grading-tables>.

8.3.7.1 Grade 1 Creatinine Abnormality: Serum creatinine of 1.1 to 1.3 x ULN

- WITHHOLD further doses of cemiplimab/placebo until clinical and laboratory evaluation are completed and diagnosis and etiology of the symptoms or laboratory abnormalities are defined
- Ensure participant is well-hydrated and repeat serum creatinine
- Obtain urinalysis, erythrocyte sedimentation rate (ESR), complement levels (C3, C4, CH50), anti-DNA levels, and antineutrophil cytoplasmic antibody (ANCA)
- Monitor serum creatinine weekly until it returns to <1.1 x ULN

8.3.7.2 Grade 2 Creatinine Abnormality: Serum creatinine of  $>1.3$  to  $1.8 \times$  ULN OR increase to  $1.3$  to  $<1.5 \times$  participant's baseline

- WITHHOLD further doses of cemiplimab/placebo until clinical and laboratory evaluation are completed and diagnosis and etiology of the symptoms or laboratory abnormalities are defined
- Immediately contact the core team via email at [[contact]](mailto:[contact])
- Ensure participant is well-hydrated and repeat serum creatinine
- Obtain urinalysis, erythrocyte sedimentation rate (ESR), complement levels (C3, C4, CH50), anti-DNA levels, and antineutrophil cytoplasmic antibody (ANCA)
- Monitor serum creatinine every 72 hours
- Consider renal ultrasound and 24 hour urine studies
- Consider consulting nephrologist
- Consider systemic corticosteroids (starting with 1 mg/kg prednisone or equivalent once per day or dexamethasone 4 mg orally once daily for four days); when creatinine improves to Grade 1 or less, steroid taper should be started and continued over no less than 4 weeks in consultation with a nephrologist.

8.3.7.3 Grade 3 Creatinine Abnormality:  $>1.8$  to  $<3.5 \times$  ULN OR increase to  $1.5$  to  $<2.0 \times$  participant's baseline

- WITHHOLD further doses of cemiplimab/placebo until clinical and laboratory evaluation are completed and diagnosis and etiology of the symptoms or laboratory abnormalities are defined
- Consult nephrologist immediately
- Obtain urinalysis, erythrocyte sedimentation rate (ESR), complement levels (C3, C4, CH50), anti-DNA levels, and antineutrophil cytoplasmic antibody (ANCA)
- Monitor creatinine every 72 hours
- Obtain renal ultrasound and 24 hour urine studies
- Initiate moderate-dose steroids (recommend prednisone 240 mg/day orally or methylprednisolone 4 mg/kg/day IV); when creatinine improves to Grade 1 or less, steroid taper should be started and continued over no less than 4 weeks in consultation with a nephrologist.
- If no response to initial corticosteroids, consider high-dose steroids (recommended methylprednisolone 1 g/day IV) in consultation with a nephrologist; high-dose corticosteroids should be tapered, if used, in consultation with a nephrologist.

8.3.7.4 Grade 4 Creatinine Abnormality:  $\geq 3.5 \times$  ULN OR increase of  $\geq 2.0 \times$  participant's baseline

- WITHHOLD further doses of cemiplimab/placebo until clinical and laboratory evaluation are completed and diagnosis and etiology of the symptoms or laboratory abnormalities are defined

- Immediately contact the core team via email at [[contact]](mailto:[contact])
- Consult nephrologist immediately
- Obtain urinalysis, erythrocyte sedimentation rate (ESR), complement levels (C3, C4, CH50), anti-DNA levels, and antineutrophil cytoplasmic antibody (ANCA)
- Monitor creatinine every 72 hours
- Obtain renal ultrasound and 24 hour urine studies
- Initiate high-dose steroids (recommended methylprednisolone 1 g/day IV) in consultation with a nephrologist; high-dose corticosteroids should be tapered, if used, in consultation with a nephrologist.

